2.3.2. Benefit Assessment

AtD participants may experience benefit in improved symptoms and clinical presentation following a single administered dose of GSK1070806. By enrolling in this study, participants will be contributing to the process of developing a new medicine to address the unmet need for patients intolerant or unresponsive to currently available treatments.

2.3.3. Overall Benefit: Risk Conclusion

[figure not shown]
There remains an unmet medical need for effective treatment of AtD in patients who inadequately responded to topical SoC.

Considering the measures taken to minimise the potential risks of GSK1070806, the potential for clinical benefit outweighs the potential risks of testing GSK1070806 in study participants.

3. OBJECTIVES AND ENDPOINTS

| Objectives | Endpoints |
|--|--|
| Primary | |
| To compare the clinical effect of a single intravenous (IV) infusion of 2 mg/kg of GSK1070806 versus placebo in moderate to severe Atopic Dermatitis in the Biologic Naïve (BN) population (Group 1). | Percent change from baseline (PCFB) in the Eczema Area and Severity Index (EASI) at Week 12 (Section 8.1.1). |
| Secondary | |
| To further compare the clinical effect (GSK1070806 versus placebo) in the BN population (Group 1). | Change from Baseline (CFB) in the EASI at Week 12. EASI 50/75/90 defined as ≥ 50/75/90% reduction in the EASI from Baseline at Week 12. Investigator Global Assessment (IGA) score of 0 or 1 at Week 12. |
| To estimate the clinical effect of GSK1070806 in the dupilumab inadequate responder (Dupi-IR) population (Group 2). | PCFB in the EASI at Week 12. |
| To assess safety and tolerability (GSK1070806 versus placebo) in the combined AtD population (Groups 1 and 2). | Incidence of serious adverse events (SAEs) and adverse events (AEs). Incidence of clinically important (1) findings in: |

| Objectives | Endpoints |
|---------------------------------|---|
| | vital signs |
| | electrocardiogram |
| | laboratory: haematology, clinical |
| | chemistry and urinalysis. (Section 8.3) |
| To assess anti-drug antibody | Incidence of ADAs (Section 8.8) |
| (ADA) formation in the combined | |
| AtD population (Groups 1 and 2) | |

| Objectives | Endpoints |
|------------|-----------|

1) Absolute or change in important clinical findings are defined in the statistical analysis plan (SAP) for each relevant safety endpoint.

4. STUDY DESIGN

4.1. Overall Design

This is a multi-centre, 12-week, randomized, double-blind, parallel group, placebo-controlled study of GSK1070806 administered as a single 2 mg/kg IV and will investigate the efficacy and safety in moderate-severe AtD participants. See the Study Schematic (Section 1.2) and the Schedule of Activities (Section 1.3).

Study Populations and Randomisation

Group 1 - BN: for whom disease was not adequately controlled by topical treatments. Approximately 40 BN patients may need to be consented for screening to provide 30 randomized. Thirty BN participants will receive GSK1070806 or placebo in a 2:1 ratio (20 and 10 participants, respectively).

Group 2 - Dupi-IRs: patients whose disease was not adequately controlled following at least 16 weeks of dupilumab treatment (please refer to inclusion and exclusion criteria) or who could not tolerate dupilumab. Approximately 24 Dupi-IR patients may need to be consented for screening to provide 18 randomized. Eighteen Dupi-IR participants will receive GSK1070806 or placebo in a 5:1 ratio (15 and 3 participants, respectively).

Primary Efficacy Endpoint

The primary efficacy endpoint is percent change from baseline in the eczema area and severity index (PCFB EASI [Hanifin, 2001]) at Wk 12 in participants of Group 1.

Study Duration

Groups 1 and 2 will be conducted in parallel.

The overall study duration for an individual participant is not expected to exceed 28 weeks (Screening is 4 weeks; Treatment Period is 12 weeks; Follow-Up Period is 12 weeks).

The End of Study (Wk 24, Day 169) allows for continued safety monitoring beyond the Wk 12 primary endpoint in this new disease population (AtD), for which GSK1070806 has not yet been tested.

Treatment and Follow-Up Periods Screening Period

- The Screening Period is 28 days.
- All participants must stop using topical treatments (corticosteroids, calcineurin inhibitors or Phosphodiesterase 4 [PDEIV] inhibitors) for at least 7 days (starting on Day -7) prior to dosing on Day 1.
- Participants should apply bland topical emollient at least once from at least Day -7 (until at least Wk 12).
- Participants must record itch (PP-NRS) and fatigue (brief fatigue inventory, item 3) daily starting on Day -7 (see SoA Section 1.3).

Following the end of the single intravenous infusion of study treatment, participants are to be monitored for at least a two-hour period before discharge from the clinical unit.

The Treatment and Follow-Up Periods are both 12 weeks in duration. The participant will be instructed to make contact with the site at any time in case of any concern. Participants who withdraw from the study must be encouraged to complete the assessments listed for the Withdrawal Visit.

Safety Review Team (SRT)

In line with routine pharmacovigilance, an internal GSK safety review team (SRT, see Section 10.1.5) will have oversight of any emerging safety data related to GSK1070806 and will review *blinded* safety data at appropriate intervals.

Statistical Analyses

- The primary analysis will be performed when all participants in Group 1 have reached Wk 12 (or have withdrawn from the study prior to Wk 12).
- Interim analyses may be performed in Groups 1 and 2, and will be overseen by a Data Review Committee (DRC, Section 10.1.5):
 - Oroup 1: One unblinded efficacy interim analysis may be performed when approximately 50% participants in Group 1 have completed Wk 12 (or have withdrawn prior to Wk 12, see Section 9.5.2). The study may be terminated following the interim analysis. Additional unblinded interim analyses may be performed to support internal decisions and will have no impact on the conduct of the study.
 - Group 2: One unblinded efficacy interim analysis may be performed when approximately 30 participants in Group 1 have been randomized (Section 9.5.2). Group 2 recruitment may be terminated following the interim analysis. Additional unblinded interim analyses may be performed to support internal decisions and will have no impact on the conduct of the study.
- An end of study analysis will be performed when the last participant last visit (LPLV)
 has been achieved.

4.2. Scientific Rationale for Study Design

Randomized, double-blind, placebo-controlled design

GSK1070806 is an experimental drug which has not previously been studied in the AtD population. The inclusion of a placebo arm in Groups 1 and 2 will ensure blinding of any attribution of treatment to potential safety signals whilst also providing control data for the comparison of efficacy and biomarkers.

Rationale for Two Study Populations

Participants are to be grouped on the basis of their prior treatment: *either* Group 1 - biologic naïve (BN) and having failed topical therapies, *or* Group 2 - whether having specifically demonstrated an inadequate response to dupilumab (Dupi-IR).

• Group 1: Participants with moderate to severe AtD who have not responded adequately to topical treatments (after 4 weeks treatment with either TCS or TCI within the last 6 months) may usually, at this stage, be considered for an approved therapy (if available) e.g. Dupixent, or JAKis, or be considered for clinical trials.

Potential BN participants must not have ever been treated for AtD with either dupilumab, other experimental biological treatments, or JAKi(s), owing to the potential for an overlapping mechanism of action with GSK1070806

Studying GSK1070806 in the BN population will enable evaluation of preliminary efficacy in moderate-severe AtD and will allow indirect comparison with historical data.

• Group 2: Although approximately 50% AtD patients receiving dupilumab (Dupixent, an anti-interleukin-4 receptor [IL-4R] mAb) achieve EASI75, there remains a significant unmet need. Since the range of biological processes impacted by IL-18 is broader than those impacted by IL-4/IL-13, there is the potential that GSK1070806 may provide benefit to those patients who were not adequately controlled by dupilumab. Therefore, it is of particular interest to additionally select/include a small group of Dupi-IRs to broaden the investigation.

Given the putative difference in efficacy between the two study populations (as a consequence of prior treatment with dupilumab), the clinical endpoints for these populations are to be analysed separately (see Section 9).

Washout of prior therapy during Screening.

All participants must meet all clinical criteria at the point of randomization (for subsequent dosing on Day 1) following at least a 7-day washout of TCS (starting from Day -7).

Duration of Treatment / Follow-Up Period

The duration of the Treatment Period is 12 weeks (see both this Section 4.2 "Efficacy Endpoints" and Justification for Dose: Section 4.3).

The duration of the Follow-Up Period is based upon the observed half-life of GSK1070806 in healthy volunteers, which was 31 days at 1mg/kg and 38 days at 3mg/kg [Investigator's Brochure: GSK Document Number WM2009/00047/07]. Following patients for 24 weeks after administration of GSK1070806 allows safety monitoring to continue for approximately 5 half-lives in this new disease population (see Justification for Dose, Section 4.3).

Randomization Ratio

Group 1 (BN): participants will be randomized in a 2:1 ratio to increase the overall chance of participants receiving GSK1070806 over placebo. To supplement the number of participants in the placebo arm, historical data were used and a robust meta-analytic predictive (MAP) prior was constructed with an effective sample size of 14 participants (expected local-information-ratio [ELIR] method [Neuenschwander, 2020]).

Group 2 (Dupi-IR): participants will be randomized in a 5:1 ratio. The clinical effect in this group will not be compared against placebo (see Section 9) but a small placebo arm has been included to maintain the study blind.

Efficacy Endpoints

The primary endpoint is PCFB in the EASI at Wk 12 in the BN population (Group 1).

[figure not shown]
EASI (see Section 8.1.1) is a precedented composite clinical endpoint for use in early clinical trials of moderate to severe AtD [Hanifin, 2001]. The magnitude of efficacy (measured as PCFB and CFB EASI) observed as clinically meaningful was evident by 12 weeks after administration of both marketed products (Crisaborole [Bissonnette, 2019], Dupixent [Beck, 2014] and of Phase II/III experimental drugs, Upadacitinib [Guttman-Yassky, 2020] and Abrocitinib [Simpson, 2020b] and will allow for indirect comparison to other therapies.

Similarly, the IGA response is an established Food and Drug Administration (FDA) regulatory endpoint. Clinical scores will be measured throughout to ensure preliminary assessment of the onset, extent and duration of clinical response.

Patient Reported Outcomes (PROs)

Nearly two-thirds (62·9%) of moderate to severe AtD patients report itching for at least 12 h each day, with 60·5% of patients rating their itch as either severe or unbearable (Simpson, 2016c). Reducing the itch–scratch cycle is an important treatment goal and forms a key aspect of reducing overall disease severity. The PP-NRS is a recognized clinical instrument for itch in AtD (reviewed Yosipovitch, 2019). Three additional PRO instruments have been introduced to collect qualitative and meaningful data on sleep disturbance. Lei 2020) and [Tennant, 2019] and [Mendoza, [Mendoza, 12]]

[Tennant, 2019] and [Mendoza, 1999]). The dermatology life quality index (DLQI) covers the impact of AtD on general aspects of daily living [Finlay, 1994], see details in Section 8.2.

TMF-14679521 **CONFIDENTIAL** 215253

4.2.1. Participant Input into Design

Feedback on study design obtained during interview with one patient based in US held on 22-04-021. Based on the patient feedback from the interview, the number of biopsies was decreased from 5 to 4.

4.3. Justification for Dose

A single 2 mg/kg dose GSK1070806 administered via intravenous infusion is proposed for Study 215253.

The predicted exposures of GSK1070806 (Cmax and AUC; 0.05 mg/mL and 27.2 mg.h/mL, respectively) after a single dose of 2 mg/kg are 376 and 65 fold below the NOAEL thresholds (Cmax and weekly AUC; 18.8 mg/mL and 1775 mg.h/mL, respectively) from the 1 month cynomolgus monkey study (4 weekly 300 mg/kg doses).

The safety, tolerability and PK of GSK1070806 have been evaluated in humans after administration of a single escalating dose (dose level ranging from 0.008 mg/kg up to 10 mg/kg) and after two doses administered 28 days apart (dose levels studied: 0.25 mg/kg or 5 mg/kg). In all clinical studies to date, GSK1070806 was well tolerated over at least 210 days (see Investigator Brochure [GSK Document Number WM2009/00047/07]).

A mechanistic PKPD model based on both preclinical affinity data and the observed clinical PK and PD data suggests that a single 2 mg/kg dose GSK1070806 administered via intravenous infusion is anticipated to provide >90% reduction in plasma free IL-18 levels in at least 90% of participants for at least 12 weeks: this extent and duration of inhibition is judged to be sufficient to provide a robust assessment of the potential of GSK1070806 to treat AtD.

GSK1070806 has a terminal half-life ranging from 31 to 38 days after single dose administration of 1 or 3 mg/kg. Therefore, it is expected that after a single dose of 2 mg/kg, drug levels at the End of Study (Day 169) will be reduced 32-fold (2⁵) as compared to the C_{Max} at the end of infusion. Although the concentration of GSK1070806 at Day 169 is predicted to be >10,000 fold below the NOAEL threshold, the extended pharmacodynamic effect observed in previous studies suggest that circulating GSK1070806 at this time may still retain some pharmacological activity. However, in previous clinical studies, GSK1070806 was well tolerated over at least 210 days after dosing when compared to placebo at doses up to 10mg/kg, so safety monitoring for a 24-week period in this study is appropriate.

4.4. End of Study Definition

The End of Study is defined as the date of the last visit of the last participant according to the Schedule of Activities.

A participant is considered to have completed the study if he/she has completed the last scheduled procedure shown in the Schedule of Activities.

5. STUDY POPULATION

TMF-14679521

Inclusion Criteria Numbers 4 and 5 and Exclusion Criterion Number 21 distinguish the two study populations.

Prospective approval of protocol deviations to recruitment and enrolment criteria, also known as protocol waivers or exemptions, is not permitted.

5.1. Inclusion Criteria

TYPE OF PARTICIPANT AND DISEASE CHARACTERISTICS

- 1. Moderate to severe atopic dermatitis (confirmed by a dermatologist) according to the Hannifin and Rajka criteria or Eichenfield revised criteria [Eichenfield, 2014; Hanifin, 1980].
- 2. Onset of AtD symptoms occurring at least 6 months prior to Screening, with stable disease for at least 1 month prior to Screening.
- 3. The participant should meet the following criteria at the initial Screen and immediately prior to trial drug infusion on Day 1 (Baseline):
 - a. EASI≥16
 - b. IGA score >3.
- 4. Group 1 Biologic Naïve: Topical First Line Treatment: Documented recent history (within 6 months before Screening) of:
 - a. *either* an inadequate response (IR) to out-patient treatment with *at least one* topical treatment (intermittent TCS, TCI), topical PDEIV inhibitor (Crisaborole).
 - b. *or* that topical treatments were otherwise not recommended.
- 5. Group 2 Dupi-IRs: Documented history of an inadequate response (IR) to dupilumab:
 - a. **either** following at least 16 weeks of treatment according to the Investigator's judgement
 - b. *or* intolerant to dupilumab owing to adverse events.
- 6. Willing to discontinue topical corticosteroids, topical calcineurin inhibitors or topical PDEIV inhibitors from at least 7 days (starting Day -7) prior to trial drug infusion on Day 1.

- 7. Stable use of topical emollient e.g. use of an additive-free, bland emollient for at least 7 days (starting Day -7) prior to dosing on Day 1 and be willing to continue a stable regimen for at least 12 weeks after dosing).
- 8. Willing to contribute three serial 4.5 mm punch biopsies of lesional skin and a set of tape strips at Baseline, Wk 4 and Wk 12. Willing to contribute one 4.5 mm punch biopsy of non-lesional skin at Baseline.
- 9. If receiving concomitant medications for any reason, the participant should try to stay on a stable regimen throughout the entire study.

AGE

10. Between 18 and 75 years of age inclusive, at the time of signing the informed consent.

WEIGHT

11. Body mass index (BMI) within the range 18 - 39.9 kg/m² (inclusive).

SEX and CONTRACEPTIVE/BARRIER REQUIREMENTS

- 12. Sex and Contraceptive /Barrier requirements for males and females
- a. Male Participants:

Male participants are eligible to participate.

- b. Female Participants:
- A female participant is eligible to participate if she is not pregnant or breastfeeding, and one of the following conditions applies:
 - Is a woman of non-childbearing potential (WONCBP) as defined in Section 10.4, Contraception and Barrier Guidance.

OR

- O Is a woman of childbearing potential WOCBP and using an acceptable contraceptive method as described in Section 10.4 during the study period. The investigator should evaluate the potential for contraceptive method failure (e.g., noncompliance, recently initiated in relationship to the first dose of study intervention.
- A WOCBP must have a negative highly sensitive serum pregnancy test result (as required by local regulations) at the initial Screening visit and a negative urine pregnancy test result immediately prior to dosing on Day 1: see Section 8.3.5 Pregnancy Testing.

- [If a urine test cannot be confirmed as negative (e.g., an ambiguous result), a serum pregnancy test is required. In such cases, the participant must be excluded from participation if the serum pregnancy result is positive.]
- Additional requirements for pregnancy testing during and after study intervention are located in Section 8.3.5.
- The investigator is responsible for review of medical history, menstrual history, and recent sexual activity to decrease the risk for inclusion of a woman with an early undetected pregnancy

INFORMED CONSENT

TMF-14679521

13. Capable of giving signed informed consent as described in Section 10.1 which includes compliance with the requirements and restrictions listed in the informed consent form (ICF) and in this protocol.

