1. PROTOCOL SUMMARY

1.1. Synopsis

Protocol Title: A Phase Ib, Randomized, Double-Blind, Parallel Group, Placebo-Controlled Study of the Clinical Effect, Safety and Tolerability of a Single Intravenous Infusion of GSK1070806 in Moderate to Severe Atopic Dermatitis Patients.

Brief Title: Clinical Effect, Safety and Tolerability of GSK1070806 in Atopic Dermatitis.

Rationale: Interleukin-18 (IL-18) is a pleiotropic cytokine with potential to amplify pathways important in Atopic Dermatitis (AtD) and for which increased IL-18 levels correlate with disease severity. GSK1070806 is a potent anti-IL-18 monoclonal antibody that is being developed for the treatment of AtD.

Objectives and Endpoints:

| Objectives | Endpoints | | | |
|---|---|--|--|--|
| Primary | | | | |
| To compare the clinical effect of a single intravenous (IV) infusion of 2 mg/kg GSK1070806 versus placebo in moderate to severe Atopic Dermatitis in the Biologic Naïve (BN) population (Group 1). | Percent change from baseline (PCFB) in the Eczema Area and Severity Index (EASI) at Week 12. | | | |
| Secondary | | | | |
| To further compare the clinical effect (GSK1070806 versus placebo) in the BN population (Group 1). | Change from baseline (CFB) in the EASI at Week 12. EASI 50/75/90 defined as ≥ 50/75/90% reduction in the EASI from Baseline at Week 12. Investigator Global Assessment (IGA) score of 0 or 1 at Week 12. | | | |
| To estimate the clinical effect of GSK1070806 in the dupilumab inadequate responder (Dupi-IR) population (Group 2). | PCFB in the EASI at Week 12. | | | |
| To assess safety and tolerability (GSK1070806 versus placebo) in the combined AtD population (Groups 1 and 2). | Incidence of serious adverse events (SAEs) and adverse events (AEs). Incidence of clinically important findings in: vital signs electrocardiogram laboratory: haematology, clinical chemistry and urinalysis. | | | |

215253

| Objectives | Endpoints |
|------------------------------|--------------------|
| To assess anti-drug antibody | Incidence of ADAs. |
| (ADA) formation in the AtD | |
| population (Groups 1 and 2 | |
| combined) | |
| | |

Overall Design:

A multi-centre, 12-week, randomized, double-blind, parallel-group, placebo-controlled study of GSK1070806 to investigate efficacy and safety in moderate-to-severe AtD participants.

Brief Summary:

The study will assess the impact of GSK1070806 in two groups of patients with moderate-to-severe AtD:

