2.1. Study Rationale

Atopic Dermatitis

Atopic dermatitis is a chronic relapsing inflammatory skin disease characterized by eczematous lesions and intense pruritus [Weidinger, 2016, Simpson, 2016a], and is associated with skin barrier dysfunction and immune dysregulation. Intense pruritus results in sleep deprivation, signs of anxiety and depression, impaired quality of life and reduced productivity [reviewed Yosipovitch, 2019].

AtD is a heterogeneous disease with primary T-helper cell (T_H)2/T_H22-skewing and variable T_H1/T_H17 contribution [Glickman, 2020]. Changes in the transcriptional profile of AtD have been observed with a number of experimental / approved therapies that have also shown clinical efficacy including cyclosporin [Khattri, 2014], topical corticosteroids [Brunner, 2016], Janus kinase inhibitors [Pavel, 2019], phosphodiesterase 4 inhibitor [Bissonnette, 2019] dupilumab [Beck, 2014], ustekinumab [Khattri, 2017] and fezakinumab [Brunner, 2019]. The AtD skin proteome shows an inflammatory and vascular-endothelial signature (even in non-lesional skin), emphasizing the need for early treatment [Pavel, 2019].

Prevalence and Economic Burden

Population-based estimates place adult prevalence between 2.1 - 4.4% across countries [Barbarot, 2018]. Severity is consistent worldwide with mild, moderate and severe at ~60%, ~29%, and 11%, respectively [Fuxench, 2019].

In the United States (U.S.) three recent studies report that AtD occurs in approximately 7-8% adults [Silverberg, 2015, Barbarot, 2018, Sacottte, 2018, Fuxench, 2019].

From a 2004 study investigating the burden of skin disease in the United States, it was estimated that total annual burden of AtD (direct, indirect and costs due to quality of life) was \$4.2 billion, equating to approximately \$5.4 billion in 2016 [Adamson, 2017].

Treatment(s) and Unmet Medical Need

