8.1.2. Investigator Global Assessment (IGA)

Investigator's Global Assessment (IGA) for Atopic Dermatitis is a measure of overall disease severity at the time of assessment and is the established FDA regulatory endpoint. It is measured on the following scale:

0: Clear (No inflammatory signs of atopic dermatitis)

1: Almost Clear (Just perceptible erythema and just perceptible papulation/infiltration)

TMF-14679521 **CONFIDENTIAL** 215253

- 2: Mild Disease (Mild erythema and mild papulation/infiltration)
- 3: Moderate Disease (Moderate erythema and moderate papulation/infiltration)
- 4: Severe Disease (Severe erythema and severe papulation/infiltration with or without oozing/crusting).

Please refer to the SRM for details on scoring the IGA.

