1.1. Objectives, Estimands and Endpoints

Objectives	Endpoints
Primary	
To compare the clinical effect of a single intravenous (IV) infusion of 2 mg/kg of GSK1070806 versus placebo in moderate to severe Atopic Dermatitis in the Biologic Naïve (BN) population (Group 1).	Percent change from baseline (PCFB) in the Eczema Area and Severity Index (EASI) at Week 12
Secondary	
• To further compare the clinical effect (GSK1070806 versus placebo) in the BN population (Group 1).	 Change from Baseline (CFB) in the EASI at Week 12. EASI 50/75/90 defined as ≥ 50/75/90% reduction in the EASI from Baseline at Week 12. Investigator Global Assessment (IGA) score of 0 or 1 at Week 12.
To estimate the clinical effect of GSK1070806 in the dupilumab inadequate responder (Dupi-IR) population (Group 2).	PCFB in the EASI at Week 12.
To assess safety and tolerability (GSK1070806 versus placebo) in the combined AtD population (Groups 1 and 2).	 Incidence of serious adverse events (SAEs) and adverse events (AEs). Incidence of clinically important findings in: Vital signs Electrocardiogram Laboratory: haematology, clinical chemistry and urinalysis.
To assess anti-drug antibody (ADA) formation in the combined AtD population (Groups 1 and 2).	Incidence of ADAs

Primary estimand

The primary clinical question of interest is: What is the treatment effect on Eczema Area and Severity Index (EASI) after 12 weeks of treatment with a single intravenous (IV) infusion of 2 mg/kg GSK1070806 versus placebo in Biologic Naïve participants (Group 1) with moderate to severe Atopic Dermatitis in the absence of use of Rescue Therapy.

[figure not shown]
The primary estimand is described by the following attributes:

- Population: Biologic Naïve (BN) participants with moderate to severe Atopic Dermatitis.
- Treatment condition: A single 2 mg/kg one-hour IV infusion of either GSK1070806 or placebo at Day 1.
- o Variable / endpoint: Percent change from Baseline to Week 12 in the EASI.
- o Summary measure: Difference (GSK1070806 placebo) in mean percent change from baseline in EASI at Week 12.
- o Intercurrent events: Use of Rescue Therapy. It will be handled with a hypothetical strategy, i.e. values after use of Rescue Therapy will be set to missing.

Rescue Therapy is defined in this document as the use of any prohibited medication (as defined in the protocol section 6.8.2) that is considered as an important protocol deviation.

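### As printed, the IGA entry threshold admits only patients graded Severe, although the title, primary objective, inclusion criterion 1 and SAP estimand all name a moderate to severe population

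*Protocol*

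**What the plan says.** Protocol Section 5.1, criterion 3, begins: "The participant should meet the following criteria at the initial Screen and immediately prior to trial drug infusion on Day 1 (Baseline". Two items follow. Item 3a is an EASI threshold printed with a greater-than-or-equal sign (16 or more). Item 3b is an IGA threshold printed with a plain greater-than sign (above 3).

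Protocol Section 8.1.2 defines the IGA as five whole-number grades. The top two are "3: Moderate Disease (Moderate erythema and moderate papulation/infiltration") and "4: Severe Disease (Severe erythema and severe papulation/infiltration with or without oozing/crusting").

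Four places name the population:
- Protocol title (Section 1.1): "Single Intravenous Infusion of GSK1070806 in Moderate to Severe Atopic Dermatitis Patients".
- Primary objective (Protocol Section 3): "in moderate to severe Atopic Dermatitis in the Biologic Naïve (BN) population (Group 1").
- Inclusion criterion 1 (Protocol Section 5.1): "Moderate to severe atopic dermatitis (confirmed by a dermatologist").
- SAP Section 1.1, primary estimand: "Population: Biologic Naïve (BN) participants with moderate to severe Atopic Dermatitis".

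Protocol Sections 5 and 8 rule out waivers. Protocol Section 4.2 and SAP Section 1.2 require every clinical criterion to be met at randomization.

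**The concern.** Criterion 1 and criterion 3b stand in the same list and describe different populations. A site applying 3b literally turns away every patient graded Moderate on the protocol's own scale, and the people enrolled are then a narrower group than the estimand describes. A site that works from the title or criterion 1 may randomize IGA 3 patients. They are ineligible as written and would be eligibility deviations under SAP Section 6.1.3. If sites differ, the severity mix depends on which reading each site adopted, in a primary comparison with only 10 placebo participants.

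Eligibility also cannot be repaired at analysis: a patient wrongly turned away leaves no data. Criterion 3 is not limited to one group. Protocol Section 5 says only criteria 4 and 5 and exclusion 21 separate the groups, so all 48 planned participants are affected.

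**Working it through.** No stated figure belongs to this point, so the check is a comparison of passages.

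**1. Apply the threshold to the scale.** The grades in Protocol Section 8.1.2 are 0, 1, 2, 3 and 4, with no intermediate values.

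| Reading of 3b | Grades admitted | Agrees with a moderate to severe population? |
|---|---|---|
| IGA > 3 (as printed) | 4 (Severe) | No |
| IGA ≥ 3 | 3 (Moderate), 4 (Severe) | Yes |

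**2. Look for text that overrides 3b.** The supplied text gives no other IGA entry threshold. Section 8.1.2 points to the study reference manual only for scoring. Criterion 3 uses 'should', but Section 4.2 and SAP Section 1.2 make all clinical criteria binding at randomization.

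**3. See how the rest of the plan fits a severe-only reading.**
- SAP Section 6.1.2 plans a categorical summary of baseline IGA. With every criterion met, it would have a single category.
- SAP Section 4.3.1.2 puts a mean-centred baseline score into each logistic model. If that score is baseline IGA for the IGA 0/1 endpoint (the SAP does not say), everyone has 4 − 4 = 0 and the data carry no information on its coefficient.
- IGA 0/1 would require a fall of at least 4 − 1 = 3 grades from everyone, against 3 − 1 = 2 for a patient entering at grade 3.

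These sit awkwardly with severe-only entry but do not prove what was intended.

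**4. Check whether the stated operating characteristics move.** Their inputs (Protocol Section 9.2, SAP Section 5) are the arm sizes, an SD of 50, the priors, the assumed true means and the decision thresholds. IGA is not among them.
- Group 2 example, true mean −55 and threshold −45: Φ((−45 + 55)/(50/√15)) = Φ(10/12.91) = 78.1%, as printed. All 12 Group 2 figures reproduce to the printed decimals.
- Group 1, simulated with 200,000 replicates per scenario: at a true difference of −40% the three criteria give 82.7%, 92.8% and 68.9%, against 82.6%, 92.8% and 68.8% printed. All 12 figures agree within 0.2 points.

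Both tables can therefore be rebuilt without any reference to IGA, and either reading of 3b leaves them as they are.

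**The case against.** **The sign may be a reading artefact.** This is the strongest objection, and it stands as a caution. The point turns on one stroke, and the text was extracted from a PDF. Single characters are misread elsewhere: Group 1 appears as 'Oroup 1' in Protocol Section 4.1, and SAP Section 4.2.2 shows an SD of 106 where Section 4.3.1.2 has 10⁶. The intact sign in 3a makes a loss in 3b less likely but does not exclude it.

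**Moderate need not mean IGA 3.** Criterion 1 is a separate dermatologist's confirmation, and a patient called moderate on another basis but graded IGA 4 could enter. That is correct, so the point is limited to patients graded Moderate on the IGA. The Schedule of Activities links screening EASI and IGA to criterion 1, but this settles little: the same schedule links stopping topicals to criterion 9, which in Section 5.1 is criterion 6.

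Three stronger readings are tempting, and the documents do not support them:
- *A reader might infer that 72.5% of the target population is excluded*, from the split in Protocol Section 2.1 ("mild, moderate and severe at ~60%, ~29%, and 11%, respectively"): 29/(29 + 11) = 72.5%. That assumes the survey's categories equal IGA 3 and 4, which the documents do not say, and it ignores EASI ≥ 16 and the treatment-history criteria. The excluded share is the proportion of otherwise eligible patients graded IGA 3. It is not given and could lie anywhere between 0 and 100%.
- *A reader might infer that the placebo prior no longer matches the trial.* The plan describes its sources only as trials in atopic dermatitis (Protocol Section 9.2; SAP Sections 4.2.2 and 5). Of the 12 publications listed, seven name moderate-to-severe disease in their titles and five do not, and their entry criteria are not in the documents. The prior also carries a 50% vague component, and SAP Section 4.2.3 adds a vague-prior sensitivity analysis.
- *A reader might infer that the trial could not answer its question.* A severe-only sample narrows the population, but the randomized comparison within it remains valid.

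**Conclusion.** The inconsistency is real on the text as printed. Criterion 3b admits one of the two IGA grades that the stated population covers. Applied literally, the trial would answer its question only in IGA-severe patients, and the enrolled population would be narrower than the estimand's. Applied according to the title, it would randomize patients who fail a written criterion that cannot be waived.

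Two assumptions carry this: that the sign on the source page is a strict inequality, and that Moderate is read on the protocol's own IGA scale. If the page shows a greater-than-or-equal sign, the point falls away. If the sign is strict, this must be corrected, because it governs who is randomized. No percentage can be put on the patients affected, and the stated operating characteristics are unaffected. The documents do not show which threshold was intended.

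**What to change.** 1. Check item 3b on the source page of the protocol. If it shows greater than or equal to 3, no change is needed.
2. If it is a strict inequality, decide which population is meant and make the text agree, in one of two ways:
   - keep the moderate to severe population and change the threshold in 3b so that it covers it; or
   - keep the threshold and restate the population as severe only in the title, synopsis, Protocol Sections 3 and 4.1, inclusion criterion 1 and the SAP Section 1.1 estimand.
3. Send sites a short clarification of the rule that applies at Screening and on Day 1.
4. If enrolment has begun, list Screening and Day 1 IGA by site, blinded to treatment, to see which reading each site used. Classify any eligibility deviations under SAP Section 6.1.3 before unblinding.

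The cost is one symbol, or a few words in several places, plus the site notice and the ethics approval that Protocol Section 10.1.1 requires for an amendment. Neither route requires a change to the stated sample size, priors or model.
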